8.5 Does this study only involve the use of existing/retrospective data/specimens?

Check yes or no.

No

8.6 Describe in detail the study design also known as the experimental flow. Include all study procedures a subject will go through, in order of sequence and timing, including frequency of visits, duration of visits, length of subject participation etc. Please Note this needs to be written for an educated person who is not an expert in the field, do not exceed 300 words:

This is also known as NIH Experimental Procedure section or Clinical Trial Procedure/Experimental Flow section. Do not just attach documents in response to this question you must do a study design summary for IRB Review.

The duration of each subject's participation will be ~4 months.

Visit 1 – Consent/Eligibility: Consent form signed; assessed for eligibility per inclusion/exclusion criteria; MMSE administered; BDI, PCS & FABQ administered; medical history, demographics, comorbidities, and medication use recorded; blood drawn for INR (in applicable subjects); pregnancy test (in applicable subjects). (~3.5 hrs)

Visit 2 – Baseline Outcomes Assessment: Study outcome measures (see Outcomes Assessment) administered to establish baseline levels. (~4 hrs)

Visit 3 - Sprint MicroLead (Electrode) Implant Procedure: Testing of muscle response with Sprint Test Needles; Implantation of percutaneous Sprint MicroLead. Subject given instructions on care of Lead exit site. Skin checked, subject queried for medication usage. Randomization to treatment group. Subset of study outcome measures (questionnaires only) administered. (~2.5 hrs)

Visit 4 - 48-72 hour Post-Implant Safety Check: Check the Lead exit site within 48-72 hours of the Implant procedure; dressing changed. (~1 hr)

Visit 5 - Start of Stimulation: Collection of parameter data; programming of external stimulator (Sprint Stimulator). Subject given instructions on use of System and care of Lead exit site. Skin checked, dressing changed, subject queried for medication usage and adverse events. Subset of study outcome measures (BPI-SF only) administered. (~2 hrs)

Phone Call #1 – One week after starting stimulation, subject queried on condition of Lead exit site, pain, adverse events. (30 min)

Phone Call #2 – Two weeks after starting stimulation, subject queried on condition of Lead exit site, pain, adverse events. (30 min)

Visit 6 - EOT Outcomes Assessment & Explant Procedure: Study outcome measures administered (4 weeks post-Implant). PGIC administered. Skin checked, subject queried for medication usage and adverse events. Lead Removed. X-rays performed (may be done as separate clinical visit). (~4.5 hrs)

Phone Call #3 - 1 week Post-Explant Safety Check: Subject queried on condition of Lead exit site. (15 min)

Visit 7 - 8-wk Outcomes Assessment: Subset of study outcome measures

(questionnaires only) administered (8 weeks post-Implant (4 weeks post-EOT)).
Subject queried for medication usage. (~1 hr)

Visit 8 - 12-wk Outcomes Assessment: Subset of study outcome measures
(questionnaires only) administered (12 weeks post-Implant (8 weeks post-EOT)).
Subject queried for medication usage. (~1 hr)

Visit 9 - 16-wk Outcomes Assessment: Study outcome measures administered (16
weeks post-Implant (12 weeks post-EOT)). Subject queried for medication usage.
(~4 hrs)

Provision for lead replacement: If, in the judgement of the Investigator, the Sprint
MicroLead becomes significantly displaced or fully dislodged, it is possible that the
Investigator may elect to place another lead which would require an unscheduled
visit and additional 48-72 hour safety check. Other visits may be repeated as
appropriate.

Unscheduled Visits are conducted if/as needed.

8.7 Please attach study design/subject visit schedule here:

Name	Description
PNS Dose for HSP Visit Schedule Table (06-14-2017) History	

*If you have an
electronic schedule of study visits
and/or procedures please attach
here.*

View: 09-00 Inclusion/Exclusion Criteria

9.0 Inclusion/Exclusion Criteria:

9.1 What are the inclusion criteria? Put this information in bullet form:

- shoulder pain localized to the glenohumeral joint, subacromial area or deltoid insertion associated with: a) rest; b) passive abduction or external rotation range of motion (ROM); c) active abduction ROM; or, d) manual palpation;
- shoulder pain onset or worsening after the most recent stroke;
- weakness of shoulder abductors ($\leq 4/5$ on MRC if isolated movement is present);
- ≥ 21 -yrs old; < 90 -yrs old;
- time of stroke ≥ 3 -mo;
- duration of HSP ≥ 3 -mo;
- HSP with moderate to severe pain (BPI SF-3 ≥ 4);
- cognitive and communication ability to fulfill study requirements (cognitive ability based upon a score of ≥ 24 on the Mini Mental Status Exam (MMSE));
- availability of reliable adult who can assist with study procedures if necessary;
- willing and able to report shoulder pain and other conditions and complete study visits throughout the 4 month study period.

Please list inclusion criteria.

9.2 What are exclusion criteria? Put this information in bullet form:

- **joint or overlying skin infection or history of recurrent skin infections;**
- **insensate skin;**
- **need to take > 1 opioid and > 1 nonopioid analgesic medication for HSP;**
- **regular intake of pain medications for another chronic pain;**
- **botox injection or subacromial steroid injections to the shoulder within the past 12 wks;**
- **receiving OT or PT for HSP;**
- **bleeding disorder or INR > 3.0 ;**
- **sensitivity to skin surface electrodes and/or medical-grade adhesives, gels, tapes;**
- **medical instability;**
- **pregnancy;**
- **uncontrolled seizures (> 1 /mo for 6-mo);**
- **history of cardiac arrhythmia with hemodynamic instability;**
- **history of lidocaine allergy;**
- **history of Parkinson's disease, SCI, TBI, MS, or ipsilateral UE lower motor neuron lesion;**
- **history of complex regional pain syndrome, myofascial pain syndrome, other pain conditions (investigator discretion);**
- **cardiac pacemaker or other implanted electronic device;**
- **history of valvular heart disease (artificial valves, requiring antibiotics for procedures, etc.);**
- **severely impaired communication;**
- **history of compromised immune system (i.e., recently or actively taking immunosuppressive therapies, AIDS) congenital immunodeficiency, or any other cause for compromised immune system with which participation would pose excessive risk.**

Please list exclusion criteria.

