Protocol: Peripheral Nerve Stimulation for Shoulder Pain: Dose Response

ID: IRB16-00510

NCT02928055

Document Date: 12/18/2020

8.0 Methods and Procedures I:

8.1 Will this research involve the following Social-Behavioral Procedures:

Check all that apply.

Name _____
 Psychological Testing _____
 Surveys/Questionnaires _____

8.2 Will this research involved any of the following Medical Procedures/Considerations:

Check all that apply.

Name _____
 Collection of Biohazardous Substances _____
 Study of Human Biological Materials (i.e. Urine Collection) _____
 Investigation/Approved Devices _____
 Study of Existing Data _____
 Medical Tests, Comparisons, Evaluations _____
 Clinical Assessments (EEG, EKG, SCID, etc.) _____
 Venipuncture (Blood Draw) _____
 Use of investigational devices _____
 Psychological testing _____

8.3 Identify Data Collection types for this study:

Check all that apply.

Name _____
 Audio-Recording/Video-Recording/Photographs _____
 Chart Review - Prospective _____
 Existing/Retrospective Data/Specimens _____
 Interviews, questionnaires or psychological tests _____

Note if you are doing, recordings, Video-Recording/Photographs then subjects will need to sign the MetroHealth Audio-Video Consent form. See the IRB Forms and Templates.

View: 08-01 Methods and Procedures II

8.1 Methods and Procedures II:

8.4 * Please specify in detail the methods and procedures that are involved in this research:

If this field is not completed your protocol will not be reviewed. Do not enter N/A. Please describe what methods and procedures will be involved in this research.

Study Summary: This is a pilot RCT to explore the role of muscle contraction as a mechanism produced by peripheral nerve stimulation (PNS) to reduce hemiplegic shoulder pain (HSP). Thirty subjects will enroll and receive a 3-week course of percutaneous IM PNS at one of 3 doses. Subjects will be randomized to receive the standard IM PNS treatment (15,120 total contractions), IM PNS at half the standard dose (7,560 total contractions), or IM PNS at 1.5 times the standard dose (22,680 total contractions). Dose will be controlled by differing the stimulation time per day (3h, 6h, or 9h) while keeping constant the duty cycle of stimulation. Subjects will be followed for 12 weeks after treatment.

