PNS Treatment Protocol: After one week for lead stabilization [80], the Sprint PNS System will be programmed for stimulation. Based on over 30-yrs of experience, the Cleveland FES Center established parameters for safe and effective delivery of PNS (pulse frequency = 12 Hz; pulse amplitude = 20 mA; pulse duration = 5-200 usec (set by clinician); duty cycle = 5-sec ramp-up, 10-sec plateau, 5-sec ramp down, 10 sec off; daily stim time (randomized) = 3, 6, 9 hrs/day; total contraction dose (randomized) = 7560, 15120, 22680 contractions). [81] These parameters provide strong fused comfortable muscle contraction with minimal fatigue. [6-12, 49, 62, 71,82-84] Stimulation frequency and amplitude are fixed. The pulse duration is set to produce strong, comfortable contraction of both the middle and posterior deltoids. A balanced biphasic waveform allows an equal amount of current to flow in either phase, creating a safe net zero charge. [85] In this dose-response study, participants receive 3h, 6h, or 9h of stimulation each day. The stimulator keeps an electronic log for compliance monitoring.

Electrode and Electrode Site Surveillance and Electrode Removal: All caregivers and participants will be trained in the assessment of electrode site and the daily placement of the Sprint Pad. The caregiver conducts daily inspections to detect complications. The nurse coordinator inspects the site for infection and performs motor/sensory threshold testing for lead migration and lead integrity, respectively, at the following times: within 48-72 hrs of lead placement, at the beginning of PNS treatment, and at the end of treatment. Inspection and testing of motor/sensory thresholds and impedance may also occur anytime during the 3-wk PNS treatment period as deemed necessary. At the end of treatment, the electrode is removed by gently pulling on the external portion. All participants undergo radiographic surveillance for retained electrode fragments.

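### Randomisation at Visit 3 comes about a week before the arms can differ and before pulse duration is set by judgement, so initial contraction strength could be set with the assigned hours known

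*Protocol*

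**What the plan says.** Section 8.6 lists the visits in order. At Visit 3 the lead is implanted and then comes "Randomization to treatment group. Subset of study outcome measures (questionnaires only) administered". Visit 4 is a site check 48 to 72 hours later. Programming of the stimulator and collection of parameter data come at Visit 5. Section 8.4 (PNS Treatment Protocol) gives the interval: "After one week for lead stabilization [80], the Sprint PNS System will be programmed for stimulation".

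The contrast between arms is defined in section 8.4 (Study Summary): "Dose will be controlled by differing the stimulation time per day (3h, 6h, or 9h) while keeping constant the duty cycle of stimulation". Frequency (12 Hz) and amplitude (20 mA) are fixed. Pulse duration is left to the clinician within 5 to 200 usec, with this target: "The pulse duration is set to produce strong, comfortable contraction of both the middle and posterior deltoids". No numeric criterion is attached to it.

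Section 8.4 (Outcomes Assessment) says that outcomes are administered blind. I found no other statement of blinding or concealment in the protocol.

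**The concern.** The study asks what muscle contraction contributes to pain relief, and it means to vary only the amount of stimulation. For that contrast to be clean, the strength of each contraction should not depend on the arm. Pulse duration is the one intensity setting left to judgement, and it is first chosen after allocation. A programmer who knew the hours, or a participant who knew them and reported comfort accordingly, could shift the starting value without departing from the protocol.

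The protocol gives no reason for allocating a week before the allocation is needed. The exposure is therefore avoidable by changing the order of steps that are already planned.

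**Working it through.** No sample size or power figure bears on this point. The check concerns sequence, and whether the plan's dose measure would reveal a difference in contraction strength.

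**1. When the arms can first differ.** Allocation is at Visit 3 (8.6). Stimulation is kept off until the lead has stabilised, with one week allowed (8.4; 10.5, item 10). Programming is at Visit 5 (8.6). All steps in between are common to the arms. The gap from allocation to the first arm-specific action is about 7 days.

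**2. The plan's dose figures, reproduced.** Inputs are 3, 6 or 9 hours per day, a cycle of 5 + 10 + 5 + 10 = 30 seconds (8.4), and 3 weeks = 21 days.

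Contractions = hours × 3600 / 30 × 21

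- 3 h: 360 per day × 21 = 7,560
- 6 h: 720 per day × 21 = 15,120
- 9 h: 1,080 per day × 21 = 22,680

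All three match section 8.4. Section 21.23 describes a different cycle (2 + 16 + 2 + 10), which also totals 30 seconds and gives the same counts. The two descriptions need reconciling, but the difference does not affect this point.

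**3. What the dose figure leaves out.** Pulse duration does not enter the formula. An arm can deliver exactly its planned number of contractions and still differ from the others in contraction strength.

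**4. Latitude in the setting.** Charge per phase = amplitude × pulse duration.

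- Lower limit: 20 mA × 5 usec = 0.1 uC
- Upper limit: 20 mA × 200 usec = 4.0 uC
- Ratio: 200 / 5 = 40

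This 40-fold span is what the protocol permits. It is not an estimate of bias. The common target narrows the range used in practice by an amount the document does not give.

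**5. Whether the order could change.** The minimisation uses baseline pain, duration of pain and age (8.4, Baseline Variables and Randomization). All three are known by Visit 2. Visit 5 already includes collection of parameter data. Nothing in the protocol requires the arm to be known before pulse duration has been set.

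**The case against.** The strongest reply is that the point argues from silence. The protocol nowhere says that the arm is disclosed at Visit 3, and generating an assignment is not the same as revealing it. Section 8.6 answers a form question limited to 300 words, where concealment steps would hardly appear. The visit schedule (8.7), the outcomes and analysis file (10.4), the treatment case report forms (14.7) and the monitoring plan (section 18) are attachments that are not shown. This stands as a limit on the claim. It does not remove the point, because the timing of allocation is stated, and section 8.4, which is long and detailed, adds no safeguard at programming.

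A reader might infer that the programmer does know the arm, because the investigative team prescribes dosage through the number of pads (8.4, Percutaneous PNS System). The text does not go that far. Someone on the team must know the arm when pads are issued, but this need not be the programmer, nor come before pulse duration is set.

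A second reply is that every arm shares one target and that frequency and amplitude are fixed. That constrains the setting but does not replace it with a measurement.

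A third reply is that a later allocation protects only the starting value. This is correct: re-testing during treatment (8.4) and lead replacement (8.6) can lead to re-setting once the arm is known.

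**Conclusion.** The point holds as an avoidable opportunity for bias in the initial setting. It is of low severity and an optional improvement for a 30-subject pilot. It rests on two readings: that the visit list gives the true order of steps, and that no attachment conceals the arm until programming is complete. The size of any effect cannot be derived, and none is assumed.

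Three stronger readings are not supported:

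- **A direction.** A reader might infer that the 9-hour arm would be set more gently, since section 10.5 calls fatigue unlikely at six hours and is silent on nine. But section 8.4 lists 3, 6 and 9 hours among the settings of which it says: "These parameters provide strong fused comfortable muscle contraction with minimal fatigue". No passage ties intensity to assigned hours.
- **A compromised baseline or implant.** Baseline outcomes are taken at Visit 2, and implantation is listed before randomisation at Visit 3. Questionnaires at Visits 3 and 5 are listed after allocation, but no section shown uses them as baseline.
- **Material loss of randomised participants before stimulation.** The protocol gives no rate of loss for the stabilisation week, so this is at most a side consideration.

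**What to change.** Preferred: at Visit 5, set pulse duration by the existing criterion, record it with the parameter data, then run the minimisation and reveal the arm. A minor side benefit is that anyone lost during the stabilisation week is never randomised.

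Alternative, if Visit 3 allocation is kept: add a sentence stating that the arm is concealed from programmer and participant until pulse duration has been recorded. This protects the setting equally well but does not bring the side benefit. If an attachment already provides for concealment, it is enough to say so in section 8.4 or 8.6.

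Under either option, report pulse duration by arm, including later changes and the reason for each.

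The cost is a reordering of steps, with no extra visit or staff and no change to doses or to the setting criterion. With late allocation, pads for every arm must be on hand at Visit 5. Re-setting after re-testing or lead replacement stays unprotected under both options, which is why later changes should be reported.

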Baseline Variables and Randomization: Baseline data will be collected so that the balance of covariates across the three groups can be evaluated. Each participant will be characterized with respect to demographics, comorbidities, and medication use.

Study outcome measures (see Outcomes Assessment) will be administered to establish baseline levels. Participants are assigned to treatment groups using an adaptive randomization algorithm [76-78] to minimize group imbalances on key patient characteristics: baseline pain (>6 or ≤ 6) [79], duration of pain (≥ 18 months or < 18 months) [5], and age (≥ 55 years or < 55 years). For each assignment, the algorithm calculates the balance of these variables across the groups and makes an assignment that would result in greater balance in the variables across groups.

Percutaneous PNS System: The Sprint PNS System (SPR Therapeutics, Cleveland, OH), also known as the Smartpatch System, will be used to deliver the PNS therapy. The System consists of a small external stimulator, percutaneous lead, and pad. The external stimulator "snaps" on to the pad. The pad has an embedded power source for the System but also serves as the anode. The pad is replaced regularly based on treatment parameters, allowing the investigative team to prescribe the total dosage based upon the number of pads. The single-channel stimulator outputs a biphasic current waveform with current pulse parameter ranges that are suitable for PNS. These electrodes have been used extensively to deliver percutaneous PNS to shoulder muscles. [6-12, 62, 71]

Lead Placement Procedure: The procedure will be performed under a sterile condition. The location and depth of the electrode implant site are determined by monopolar needle stimulation with demonstration of strong contraction of both the middle and posterior deltoid muscles. [6, 9, 62, 70] The introducer loaded with the lead is inserted perpendicular to the skin surface and advanced to the depth (3-4 cm) defined by the monopolar test stimulation. The introducer is then withdrawn with the electrode retained in the muscle by a barb at its tip.

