Additional testing was conducted in 5 subjects to validate the design of the Smartpatch Stimulator and other external components. This design validation of a non-stimulating Smartpatch System provided evidence that the Smartpatch System meets user needs regarding usability and comfort. Physical aspects of system usage, such as making cable connections, attachment between Stimulator and Pad, and attachment to the skin, were reported as easy and acceptable. Software aspects of the Smartpatch Stimulator usage, such as starting and stopping stimulation, identifying the battery level, and adjusting stimulus intensity were all reported as easy and acceptable.

Furthermore, a stimulating Smartpatch System has been used by 3 subjects to date in an ongoing IDE study being conducted under G090085. In this protocol, the system is used in the Trial Stage for determining eligibility for our implantable system. All three subjects completed the Trial Stage and were able to use the Smartpatch components successfully to deliver their stimulation therapy. Subjects completed satisfaction surveys upon completion of Smartpatch System use. All three subjects reported that it was easy to understand how to use the Smartpatch System and that the System was easy to operate. Two subjects reported that the pad wasn't sticky enough, sometimes causing them to use more than one Pad per day. Subjects in the proposed study will be given more guidance on the proper preparation of the skin to ensure pad adhesion. The subjects reported that the covering bandages used were of an acceptable adhesion and size, but two subjects reported that the Lead Connector Tapes were difficult to use. All three subjects reported that the system as comfortable, "not at all" bothersome to wear, and that they were comfortable going out in public with the system on. The subjects reported that they were satisfied with their experience in the study, felt that the study had a positive impact on their lives, and would recommend participation in the study to a friend.

21.22 Please list all research personnel authorized to use the study device:

Name	Employer	Department	Employer Name
[name]	Metro	PM&R	The MetroHealth System
[name]	MHS	Physical Medicine and Rehabilitation	Physical Medicine and Rehabilitation
[name]	MHS	SCI Consortium	The MetroHealth System
[name]	Metro	Physical Medicine and Rehabilitation	Case Western Reserve University
[name]	Metro	PM&R	The MetroHealth System

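### Hours of stimulation per day are the whole randomised contrast, yet neither scheduled call in the 3-week home course lists a usage check and no visible section says when the compliance log is read

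*Protocol*

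**What the plan says.** **The contrast.** The Study Summary in 8.4 states: "Dose will be controlled by differing the stimulation time per day (3h, 6h, or 9h) while keeping constant the duty cycle of stimulation". The PNS Treatment Protocol in 8.4 adds "Stimulation frequency and amplitude are fixed" and gives "total contraction dose (randomized) = 7560, 15120, 22680 contractions". Pulse duration is set individually for a comfortable contraction and does not define an arm.

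**Contacts during the course.** In 8.6, Visit 5 starts stimulation and Visit 6 is the end-of-treatment assessment and lead removal. Between them 8.6 schedules only Phone Calls #1 and #2, of 30 minutes each. Call #1: "One week after starting stimulation, subject queried on condition of Lead exit site, pain, adverse events". Call #2, a week later, has the same content. The Visit 6 entry lists outcomes, PGIC, skin check, medication and adverse-event queries, lead removal and X-rays. It does not list a log download.

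**Usage data.** 8.4 and 21.23 both say: "The stimulator keeps an electronic log for compliance monitoring". Neither says when it is read, by whom, or what follows. Both also describe pad supply as "allowing the investigative team to prescribe the total dosage based upon the number of pads". Section 21.21 reports that two of three users in another study found the pad insufficiently adhesive, "sometimes causing them to use more than one Pad per day".

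**Other review points.** Extra in-course inspection under 8.4 is discretionary and covers the site, thresholds and impedance. The team's review of adverse events and study data (18.01, item 3.B.2) is at least quarterly, an interval that may exceed the whole course.

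**The concern.** Participants run the stimulator themselves for 21 days. The protocol gives them legitimate ways to use it less than assigned: they may switch it off if it hurts (10.5, item 10) or discontinue if it is too uncomfortable (10.5, item 15). If such under-use is heavier where more hours are assigned, the arms move toward each other in delivered dose.

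As 8.6 is written, nobody is scheduled to notice this while it can still be put right. Once the lead is out, knowing the delivered hours helps interpretation but cannot restore the separation between arms. With 30 participants in total there is little margin for dilution.

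By comparison, medication use has a diary (8.4, Concomitant Therapies) and is queried at six visits in 8.6 (Visits 3, 5, 6, 7, 8 and 9). A background variable is thus tracked more explicitly than the randomised one.

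**Working it through.** **1. Reproduce the stated doses.** Inputs from 8.4: "duty cycle = 5-sec ramp-up, 10-sec plateau, 5-sec ramp down, 10 sec off", and a 3-week (21-day) course.

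- Cycle = 5 + 10 + 5 + 10 = 30 s, so 3600/30 = 120 contractions per hour.
- 3 h: 120 × 3 × 21 = 7,560
- 6 h: 120 × 6 × 21 = 15,120
- 9 h: 120 × 9 × 21 = 22,680

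All three match. The cycle printed in 21.23 (2 + 16 + 2 + 10) is also 30 s and gives the same totals. Delivered dose is therefore proportional to hours used. A 9 h participant who uses 6 h a day (6/9 = 67%) receives exactly the 6 h dose.

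**2. Dilution under assumed use.** The protocol gives no adherence figure, so these are assumptions, with the 3 h arm held at 100%.

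- Delivered hours = assigned hours × proportion used.
- Contrast kept = delivered difference / planned difference (6 h for 9 v 3; 3 h for the other two pairs).

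| Assumed use, 6 h / 9 h arms | Delivered h/day (3 / 6 / 9 h arms) | 9 v 3 kept | 9 v 6 kept | 6 v 3 kept |
|---|---|---|---|---|
| 95% / 90% | 3 / 5.7 / 8.1 | 5.1/6 = 85% | 2.4/3 = 80% | 2.7/3 = 90% |
| 90% / 75% | 3 / 5.4 / 6.75 | 3.75/6 = 62.5% | 1.35/3 = 45% | 2.4/3 = 80% |
| 80% / 60% | 3 / 4.8 / 5.4 | 2.4/6 = 40% | 0.6/3 = 20% | 1.8/3 = 60% |

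**3. What the 9 v 3 loss costs.** Further assumptions: effect proportional to delivered dose, and analysis by assigned arm. The sample size needed for equal power then rises by 1/(contrast kept)²: 1/0.85² = 1.38, 1/0.625² = 2.56, 1/0.40² = 6.25.

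For illustration, take 10 per arm (an assumed equal split of 30) and a two-sided 5% test by normal approximation, power = Φ(d × k × √(10/2) − 1.96). Here d is the assumed 9 v 3 effect in SD units at full use and k is the contrast kept.

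| d | k = 1 | k = 0.85 | k = 0.625 | k = 0.40 |
|---|---|---|---|---|
| 1.0 | 61% | 48% | 29% | 14% |
| 1.25 | 80% | 66% | 42% | 20% |
| 1.5 | 92% | 81% | 55% | 27% |

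The effect sizes are not from the protocol. The rows show only how quickly power falls.

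**4. Is there another in-course check?** Section 14.3 says the data collected are described in 8.4, 8.6 and 10.4. Neither 8.4 nor 8.6 contains a timed usage check, and 10.4 is an attachment that is not shown. Pad supply may limit over-use, but it does not reveal under-use, and pads replaced for poor adhesion are not a count of hours.

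**The case against.** **Silence in a short summary proves little.** The form limits 8.6 to 300 words, and it leaves out things that 8.4 requires. Threshold testing at the safety check, at the start and at the end of treatment is not named in it, nor is the medication diary. The Phone Log, Treatment CRFs, visit schedule table and monitoring plan are listed as attachments but not shown, and any of them could contain a usage question. This stands. A reader might infer that the log is never read, and the documents do not support that. They show only that no visible section fixes when it is read.

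**The adherence data are not lost.** A reader might also infer that a flat result could not be interpreted. That goes too far. The log is objective, and 21.11 says participants do not keep devices after the treatment phase, so delivered hours should be available to tell similar delivered doses from an absent dose response. What remains is the missed opportunity to correct use mid-course.

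**The size is assumed.** No section says that under-use will be greatest in the 9 h arm, and none supports over-use in the 3 h arm. Quoting only the 9 v 6 pair would exaggerate the drift, since the arms stay in order in every scenario above and 6 v 3 loses least.

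**The pad evidence is thin.** It comes from three users in another study, and 21.21 promises better guidance on skin preparation. It is enough to say that pads are a poor measure of hours, but no more.

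**Conclusion.** The point holds in a limited form. Daily hours are the only randomised variable. The two calls scheduled during the home course do not list them, and no visible section fixes when the log is read. A trial run exactly as 8.6 is written has no scheduled opportunity to correct drift before the lead is removed.

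On the assumed use patterns, between 85% and 40% of the planned 9 v 3 h contrast would remain. That range rests on full use in the 3 h arm and progressively lower use in the others, neither of which the protocol states. This is a cheap improvement to trial conduct, not a flaw that undermines the design. It closes with a cross-reference if an attachment already provides the check.

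A related inconsistency needs reconciling. The fatigue provision (item 10 in 10.5, 10.10, 18.01 item 3.B.1 and 21.24) describes split sessions that add up to six hours a day without regard to arm, which does not match the 3 h and 9 h assignments in 8.4.

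**What to change.** If the Phone Log or Treatment CRFs already record use during the course, cite them in 8.6. Otherwise:

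- **8.6, Calls #1 and #2:** add hours of stimulation per day since last contact compared with assigned hours, reasons for any difference, and re-instruction on the assigned schedule. Existing staff who do not administer the blinded outcomes should ask this. The participant's freedom to stop stimulation is unchanged.
- **8.6, Visit 6:** add download of the stimulator log and recording of delivered hours.
- **8.4 and 21.23:** state that delivered dose is reported from the log, not from pads used.
- **Fatigue provision:** reconcile the four places named above with the three assigned durations. Which wording is right is for the investigators.

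Cost: a few extra minutes on two existing 30-minute calls, one download from a returned device, a field on an existing form, and a minor amendment. The downside is slightly more contact, equal in all arms.
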